11.2.2. Regimen Selection Cohort (Cohort 2)

The objective is to compare the RSV A2 neutralizing antibody levels of all regimens containing RSV preF protein (Groups 12 through 17) to the one-dose Ad26.RSV.preF regimen (Group 11). This will be based on the estimation of GMT ratios and corresponding 95% confidence intervals (CIs) of the VNA A2 levels of the regimens containing RSV preF protein on Day 29 for the one-dose regimens (Groups 12 through 16) and on Day 85 for the two-dose regimen (Group 17) versus the VNA A2 levels on Day 29 of the one-dose Ad26.RSV.preF regimen (Group 11). The sample size was selected to provide a precision of ~0.53 on the log₂ scale.

Note: Immunogenicity data from Groups 9 and 10 of the initial safety cohort (Cohort 1) will be combined with those from Groups 16 and 17 of the regimen selection cohort (Cohort 2).

The table below presents the resulting 95% CIs for several observed ratios, assuming a standard deviation for VNA of 1 on the log₂ scale and accounting for 5% dropout.

Observed Ratio	Corresponding 95% CI
1	[0.69; 1.44]
1.2	[0.83; 1.73]
1.5	[1.04; 2.17]

In addition to the above, factors such as data from other assays, reactogenicity profiles, manufacturability and ease of administration will be considered when selecting the regimen for the expanded safety phase. A more detailed rule will be described in the Statistical Analysis Plan.

11.2.3. Expanded Safety Cohort (Cohort 3)

The expanded safety cohort (Cohort 3) should provide sufficient safety data on the selected regimen to support late stage development if the immunogenicity results of Cohort 2 are satisfactory.

Table 19 shows the probabilities of observing at least one AE in the expanded safety cohort at given true AE rates. This table shows that the current numbers give a reasonable probability to also observe less frequent events in the active groups in this cohort.

Table 19: Probability of Observing at Least One Adverse Event in the Expanded Safety Cohort (Cohort 3) at a Given True Adverse Event Rate

True Adverse Event Rate	Probability of Observing at Least One Adverse Event in N Participants		
	N=45	N=135	N=270
0.5%	20%	49%	74%
1%	36%	74%	93%
2.5%	68%	97%	100%
5%	90%	100%	100%
10%	99%	100%	100%
25%	100%	100%	100%

11.3. Participant Information

For all participants, demographic characteristics (eg, age, height, weight, body mass index, race, and gender), and other baseline characteristics (eg, physical examination, medical history, and concomitant diseases) will be tabulated and summarized with descriptive statistics. This will be done per cohort.

11.4. Immunogenicity Analyses

No formal hypothesis on immunogenicity will be tested. Descriptive statistics (geometric mean and 95% CI for ELISA and RSV neutralization assay; median and quartiles for IFN- γ ELISpot and ICS) will be calculated for continuous immunologic parameters at all timepoints. For the humoral assays, geometric mean fold rises from baseline and corresponding 95% CIs might additionally be calculated. Baseline is considered as the last available assessment before the first vaccination. Graphical representations of immunologic parameters will be made as applicable.

For categorical variables, frequency tables will be presented.

In addition, for the regimen selection cohort (Cohort 2), GMT ratios with corresponding 95% CI of the VNA A2 levels of the combination/mixture regimens on Day 29 for the one-dose regimens (Groups 12 through 16) and Day 85 for the two-dose regimen (Group 17) versus the Day 29 VNA A2 levels of the one-dose Ad26.RSV.preF regimen (Group 11) will be calculated. Therefore, a regression model will be fitted with the respective VNA A2 levels as dependent variable and the respective regimens and baseline levels as covariates, using Satterthwaite's method to calculate

the degrees of freedom and allowing different variances for the vaccines. The estimate and CIs obtained as such will be back-transformed (by exponentiation) to a GMT ratio and the corresponding CI. Note that the effect of additional factors, such as age and the interaction with the regimen, might also be explored in this model.

Note: Immunogenicity data from Groups 9 and 10 of the initial safety cohort (Cohort 1) will be combined with those from Groups 16 and 17 of the regimen selection cohort (Cohort 2).

The same model might be repeated for other assays.

In the expanded safety cohort (Cohort 3), the effect of the Month 12 and Month 24 booster will be assessed. Therefore, the following ratios for VNA A2 will be calculated:

- In the groups with an active vaccination at Month 12/Month 24, the ratio of the Month 12/Month 24 booster Day 29 level versus the prime Day 29 level with the corresponding 95% CI will be calculated.
- The groups with an active vaccination at Month 12/Month 24 will be compared to corresponding groups with placebo vaccination at Month 12/Month 24 by calculating the ratio with the corresponding 95% CI.

Note that the above might also be repeated for other assays.

The primary analysis set for the above is the PPI set. As a sensitivity analysis, key tables may also be based on the FA set. Depending on their occurrence, the effect of natural infections might be further explored.

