Group	R	N	Day 1	Day 57
11	R2	24	Ad26.RSV.preF 1×10^{11} vp + Placebo*	Placebo
12	R2	42	Ad26.RSV.preF/ RSV preF protein mixture: 5×10^{10} vp/50 μ g + Placebo*	Placebo
13	R2	42	Ad26.RSV.preF/ RSV preF protein mixture: 1×10^{11} vp/50 μ g + Placebo*	Placebo
14	R2	42	Ad26.RSV.preF/ RSV preF protein mixture: 1×10^{11} vp/150 μ g + Placebo*	Placebo
15	R2	42	Ad26.RSV.preF/ RSV preF protein mixture: 5×10^{10} vp/150 μ g + Placebo*	Placebo
16	R2	36	Separate injections* : Ad26.RSV.preF 1×10^{11} vp + RSV preF protein 150 μ g	Placebo
17	R2	36	Ad26.RSV.preF/ RSV preF protein mixture: 1×10^{11} vp/150 μ g + Placebo*	Ad26.RSV.preF/ RSV preF protein mixture: 1×10^{11} vp/150 μ g
18	R2	24	Placebo + Placebo*	Placebo
R2 TOTAL:		288		

N: number of participants (*Note*: Data from Groups 9 and 10 of Cohort 1 will be pooled with those from Groups 16 and 17 of Cohort 2 up to Month 12); R: randomization; vp: viral particles

* Each injection to be given in opposite arms

Expanded Safety Cohort (Cohort 3)

In the expanded safety cohort, approximately 315 participants will be randomized in parallel to 1 of 3 groups (Groups 19 through 21; [Table 10](#) and [Table 11](#)). No pauses in enrollment for safety assessments are planned.

Participants will receive the selected one- or two-dose regimen from Cohort 2 or placebo.

If the one-dose regimen is selected (Groups 11 through 16 from Cohort 2), Groups 19 and 20 would receive the selected regimen on Day 1, and a booster at Month 12 (the selected regimen or placebo, respectively) and Month 24 (the selected regimen). Group 21 will receive placebo at all timepoints ([Table 10](#)).

If the two-dose regimen is selected (Group 17 of Cohort 2), Groups 19 and 20 would receive the selected regimen on Day 1 and Day 57, and a booster (the selected regimen or placebo, respectively) at Month 12. Group 21 will receive placebo at all three timepoints (Table 11).

Table 10: Study Design: Expanded Safety Cohort (Cohort 3) with One-dose Regimen and Month 12 and Month 24 Booster

Group	R	N	Day 1	Month 12	Month 24
19	R3	135	Selected Regimen	Selected Regimen	Selected Regimen
20	R3	135	Selected Regimen	Placebo for the Selected Regimen	Selected Regimen
21	R3	45	Placebo for the Selected Regimen	Placebo for the Selected Regimen	Placebo for the Selected Regimen
R3 TOTAL:		315			
OVERALL TOTAL:		667			

N: number of participants; R: randomization

Table 11: Study Design: Expanded Safety Cohort (Cohort 3) with Two-dose Regimen and Month 12 Booster

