5. TREATMENT ALLOCATION AND BLINDING

Study Vaccine Allocation

Central randomization will be implemented in this study. Participants will be randomly assigned to a vaccination group based on a computer-generated randomization schedule prepared before the study by or under the supervision of the sponsor. The randomization will be balanced by using randomly permuted blocks.

In the initial safety cohort (Cohort 1), the randomization ratio in Cohorts R1a and R1c is 1:2, in Cohorts R1b and R1d the ratio is 1:2:2. In each of those cohorts, 1 sentinel participant from each group (each active group and the placebo group to maintain the blind) will initially be enrolled to monitor for any unexpected severe adverse reaction. Therefore, the randomization will be phased to accommodate this and to end up with the overall randomization ratios specified above. No stratification will be applied.

In the regimen selection cohort (Cohort 2), the randomization ratio is 4:7:7:7:7:6:6:4. No stratification will be applied.

In the expanded safety cohort (Cohort 3), stratification will be applied: participants will be assigned to 1 of 2 strata prior to randomization, depending on the blood mononuclear cell (PBMC) sampling capability and capacity of the site. One stratum will contain a maximum of 63 participants from whom blood samples to assess humoral and cellular (PBMC samples) immunogenicity will be collected. The other stratum will contain the remaining participants, from whom blood samples will be collected only for humoral immunogenicity assessments, to reach the target of a total of 315 participants in Cohort 3. Within each stratum, participants will be randomized 3:3:1 ratio to one of the respective groups.

The interactive web response system (IWRS) will assign a unique code, which will dictate the group assignment for the participant. The requestor must use his or her own user identification and

personal identification number when contacting the IWRS, and will then give the relevant participant details to uniquely identify the participant.

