9.1.5. Vaccination

On each vaccination day according to the schedules presented in Table 8, Table 9, Table 10 and Table 11, the following procedures will apply pre- and post-vaccination:

- Pre-vaccination, verification of selected inclusion/exclusion criteria,^a physical examination,^b and measurement of vital signs will be performed for all participants.
- Pre-vaccination, blood and nasal samples will be collected for immunogenicity assessments. In Cohorts 1 and 2, pre-dose blood samples will be taken on Day 1 for transcriptome analysis and safety laboratory tests (hematology and biochemistry).
- Pre-vaccination, the investigator must check for any symptoms of acute illness or fever (body temperature ≥ 38.0 °C). In such a situation, the participant may be vaccinated up to, and no later than 10 days after the scheduled vaccination, or withdrawn from further vaccination at the discretion of the investigator.
- Post-vaccination, participants will be closely observed for at least 30 minutes to monitor for development of any acute reactions, or longer if deemed necessary by the investigator. Vital signs measurement will be performed. Any unsolicited or solicited AEs and vital signs will be documented in the eCRF by study-site personnel following this observation period.
- All participants will be provided with a participant diary, thermometer, and ruler to measure and record body temperature, and solicited local and solicited systemic AEs for 7 days post-vaccination.
- Nasal swab kits and RTI Symptoms Forms will be distributed to all participants before the start of the first 2 RSV seasons of the study (relative to the enrollment date of the first participant in Cohort 1); during these RSV seasons, participants should record signs and symptoms of RTI using the RTI Symptoms Form.

^a To include receipt of any routine immunizations.

^b A full physical examination, including height and body weight, will be carried out at screening, and before final vaccination. At other vaccination visits, an abbreviated, symptom-directed examination will be performed if determined necessary by the investigator.

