9.2. Study Evaluations

9.2.1. Immunogenicity

Venous blood samples of approximately 10 mL and 50 mL will be collected for determination of humoral and cellular immune responses, respectively, at the timepoints shown in the [Schedule of Activities](#), or at the early exit visit if the participant prematurely terminates without withdrawing consent (if the early exit is at least 14 days after the previous immunogenicity blood draw).

Venous blood samples (2.5 mL) for transcriptome analysis will be collected on Day 1 (pre-dose), Day 8, and Day 15 in Cohorts 1 and 2.

All sample collection and processing will be performed by the staff at the clinical sites according to current approved standard operating procedures.

It is assumed that all participants will have a pre-existing immune response due to previous RSV exposure.

The humoral and cellular immunogenicity assays that may be used in this study (as available and applicable) are summarized in [Table 16](#) and [Table 17](#) below.

Blood for humoral and cellular immune responses will be drawn from all participants in Cohorts 1 and 2. In Cohort 3, blood will be drawn for humoral immune responses from all participants and for cellular immune responses from a subset of 63 participants.

Immunogenicity samples will be prioritized as outlined in the Laboratory Manual.

Table 16: Summary of Immunogenicity Assays (Humoral)

Assay	Purpose
Primary endpoint (Regimen Selection Cohort [Cohort 2] – Groups 11 to 15 only)	
RSV neutralization A	Analysis of neutralizing antibodies to an A strain
Secondary endpoints	
RSV neutralization A	Analysis of neutralizing antibodies to an A strain
F protein antibodies (ELISA; pre-F and/or post-F)	Analysis of antibodies binding to RSV F protein in pre-fusion and/or post-fusion form
Exploratory endpoints	
RSV strain cross-neutralization	Analysis of cross-neutralizing antibodies to B and/or a different A strain(s)
F protein antibody specificity characterization	Pre- and post-F specificity by binding or functional assays as ELISA, and/or competition ELISA. Adsorption of serum or plasma with pre-F and post-F protein before any antibody assay, epitope mapping, functional VNAs
G and/or N protein antibodies (ELISA)	Analysis of antibodies binding to RSV G and/or N protein
Adenovirus neutralization assay	Analysis of neutralizing antibodies to adenovirus

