6.1.1.1. Humoral Assays

For VNA and ELISA assays following results will be calculated: N, geometric mean[§] and corresponding 95% CI of the actual values and fold increases from baseline will be tabulated and graphically presented. *§calculate the mean and corresponding 95%CI of the log₂ transformed values, back-transform this mean [i.e. 2^{mean}] and CI [i.e. 2^{CI}].*

Actual values and fold changes from baseline are tabulated and shown as dot plots with dots for subject values, and the corresponding geometric mean and 95% CI per time point for each assay. In addition, GMT plots over time, combining the regimens in one graph (without individual subject dots) will also be created.

Ratios of actual values and of fold changes from baseline between humoral assays may also be presented.

Subject profiles of the actual values over time will be graphically presented.

Reverse distribution curves of the actual values are provided for selected time points.

In the graphs, original values will be displayed on the log₂ scale.

Scatterplots between humoral assays may be provided for the most important time points. In these scatterplots the actual values will be shown, even if they are below the LLOQ, but the LLOQ cut-off will be visualized in the graph per assay if some values are below LLOQ.

Moreover, subjects with a 4-fold increase in Ga or Gb ELISA will be considered as infected and the number of infected subjects will be summarized per period and regimen. The subject profiles of the assays against the insert will also be repeated, highlighting the infected infected subjects based on Ga or Gb ELISA

Other exploratory parameters may be analysed at the discretion of the sponsor.

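### The Cohort 3 Month 12 booster ratio (Group 19 versus 20) has no named model, and the pre-boost titre scheduled for every participant is not used

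*Protocol*

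**What the plan says.** Protocol section 11.4 treats the two cohorts differently.

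- **Cohort 2.** The GMT ratios come from a regression of VNA A2 level with "the respective regimens and baseline levels as covariates", with variances allowed to differ by vaccine, Satterthwaite degrees of freedom and back-transformation. The next provision lets this model be repeated for other assays. It does not extend it to Cohort 3.
- **Cohort 3.** Groups with an active booster "will be compared to corresponding groups with placebo vaccination at Month 12/Month 24 by calculating the ratio with the corresponding 95% CI". Nothing more is said about the estimator, and this sentence does not give a timepoint; the booster Day 29 level appears only in the bullet before it.

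The same section fixes the meaning of baseline: "Baseline is considered as the last available assessment before the first vaccination". SAP section 2.1 agrees.

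Protocol section 11 leaves specifics to the SAP. SAP section 6.1.1.1 provides, per group, the geometric mean and "corresponding 95% CI of the actual values and fold increases from baseline will be tabulated and graphically presented". The only ratios it mentions are between assays. SAP section 7.1 covers the Cohort 2 ratios only. Neither mentions a Group 19 to Group 20 ratio.

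On sampling, section 9.1.5 says for each vaccination day: "Pre-vaccination, blood and nasal samples will be collected for immunogenicity assessments". Section 9.2.1 adds: "In Cohort 3, blood will be drawn for humoral immune responses from all participants". On allocation, section 5 says that in Cohort 3 "participants will be assigned to 1 of 2 strata prior to randomization", according to site capability and capacity for PBMC sampling. That factor appears in no analysis.

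**The concern.** Group 19 versus Group 20 is the trial's randomised comparison of a Month 12 dose with placebo after the same prime, and the stated Cohort 3 objective includes determining the need for a booster. Two statisticians following the text could report different ratios and intervals: unadjusted, adjusted for Day 1, or adjusted for the pre-boost titre.

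Borrowing the Cohort 2 model as written would bring in the Day 1 titre, because that is what baseline means in these documents. The titre taken just before the booster would still be left out.

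Timing matters as well. Section 5 has the sponsor unblinded at participant level from each cohort's primary analysis. For Cohort 3 that analysis covers data to Day 29 or Day 85, before the Month 12 results. A method left open now would be chosen by an unblinded sponsor.

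**Working it through.** **Plan's own precision figure.** Protocol section 11.2.2 gives about 0.53 on the log2 scale for Cohort 2, with SD 1 and 5% dropout. Group 11 has 24 and Groups 12 to 15 have 42 each, so n = 22.8 and 39.9 after dropout. Half-width = t × SD × √(1/n₁ + 1/n₂) gives 0.529 with Welch degrees of freedom. Back-transforming 0.53 returns the three stated intervals: 0.69 to 1.44, 0.83 to 1.73 and 1.04 to 2.17. The figure reproduces.

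**Cohort 3 inputs.** Groups 19 and 20 have 135 each (Tables 10 and 11). The documents give no SD or dropout for this cohort, so SD 1 and 5% are assumed from Cohort 2: 135 × 0.95 = 128 per arm.

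**Unadjusted ratio.** 1.969 × √(2/128) = 0.246 log2, and 2^0.246 = 1.19.

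**Adjusted for the Day 365 titre.** With correlation ρ between pre- and post-boost log2 titres, equal in both arms:

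half-width = t × √[2(1 − ρ²)/128 × (1 + 1/252)]

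If the boost weakens the correlation in Group 19, the common slope β weights each arm by the inverse of its residual variance, 1 + β² − 2βρᵢ, and the half-width uses the sum of the two residual variances over 128.

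The full proposed model was also simulated: REML, separate variances by group, one common slope, a stratum term with 63/315 = 20% of each arm, and Satterthwaite degrees of freedom, with 1,500 trials per setting.

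| ρ, boosted / placebo | Closed form | Simulated | Change from 0.246 |
|---|---|---|---|
| 0 / 0 | 0.247 | 0.2465 | 0.2% wider |
| 0.3 / 0.3 | 0.235 | 0.2355 | 4% narrower |
| 0.5 / 0.5 | 0.214 | 0.2133 | 13% narrower |
| 0.7 / 0.7 | 0.176 | 0.1758 | 28% narrower |
| 0.8 / 0.8 | 0.148 | 0.1476 | 40% narrower |
| 0 / 0.8 | 0.232 | 0.2328 | 5% narrower |
| 0.2 / 0.8 | 0.217 | 0.2166 | 12% narrower |
| 0.4 / 0.9 | 0.192 | 0.1918 | 22% narrower |

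Simulated coverage was 0.943 to 0.955 adjusted and 0.943 to 0.957 unadjusted.

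**Effect on the estimate.** The SE of a chance pre-boost difference is √(2/128.25) = 0.125. At 1.96 SE the difference is 0.245 log2, and it shifts the unadjusted ratio by 2^(0.245ρ): a factor of 1.05 at ρ = 0.3 and 1.15 at ρ = 0.8, assuming equal pre- and post-boost SDs.

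**Stratum.** If stratum means differ by d log2, the gain is 1 − √(1 − 0.2 × 0.8 × d²): 0.5% at d = 0.25 and 2.0% at d = 0.5.

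**Missing Day 365 titres.** If a share m lacks the covariate, a complete-case adjusted interval is narrower than the full-sample unadjusted one while (1 − ρ²)/(1 − m) < 1, that is, while m < ρ². The limits are 9%, 25% and 49% at ρ = 0.3, 0.5 and 0.7.

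**The case against.** The strongest reply is that the text has a natural reading: an unadjusted ratio of geometric means. SAP section 6.1.1.1 sets the log2 scale and back-transformation, and with equal arms of about 128 the pooled and Welch intervals nearly coincide. That contrast is valid under randomisation. The analysis is descriptive, Cohort 3 is sized for safety, VNA A2 is secondary there, and no threshold is attached. An interval of ×/÷ 1.19 is already much tighter than the roughly ×/÷ 1.44 accepted for regimen selection in Cohort 2.

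Most of this stands. The unadjusted ratio is a reasonable default, although the SAP rule is written for single-group means, so it remains an inference. Nothing in the documents shows that a narrower interval would change a conclusion.

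It is also fair that the gain depends on a correlation the documents do not give, and that losses at Day 393 may exceed 5%. An assumed 15% loss, about 115 per arm, gives 0.260 instead of 0.246, but the percentage gains are unaffected. No document suggests that the PBMC stratum predicts titre, and no precision gain is claimed for it. A Day 547 contrast goes beyond what section 11.4 names.

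These points bear on how much the change matters. They do not supply the missing specification or make use of the pre-boost titre.

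**Conclusion.** The concern holds. Neither document names a model, covariate or stratum for the Group 19 to Group 20 ratio, and the most informative covariate already scheduled is unused. Adjusting for the Day 365 titre would narrow the interval by 4% to 40% for a common correlation of 0.3 to 0.8, and by 5% to 22% in the settings where boosting weakens the correlation. At zero correlation it costs about 0.2%. The absolute widths rest on the borrowed SD of 1 and 5% dropout; the correlations are assumptions throughout. Since there is no test and no threshold, what is at stake is the precision and reproducibility of an estimate. The change is worth making because it is cheap and fixes the method in advance.

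**What to change.** In protocol section 11.4 and SAP section 6.1.1.1, state that the Group 19 to Group 20 GMT ratio at Day 393, and at Day 547 if it is to be reported, is estimated by regressing log2 VNA A2 on:

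- group;
- log2 VNA A2 from the Day 365 pre-dose sample;
- PBMC randomisation stratum, included to match the stratified randomisation.

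Use unequal variances by group and Satterthwaite degrees of freedom, as in Cohort 2, and back-transform. Name the covariate by its day, since baseline already means the value before the first vaccination. Report the unadjusted ratio as supportive. Do not substitute the Day 1 titre for a missing Day 365 titre; participants without that sample contribute to the unadjusted ratio only.

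The cost is one model statement in each document, with no new samples or visits.
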